3 OBJECTIVES AND PURPOSE

Objective:

This is designed as a phase II study intended to evaluate the impact of sequential overlapping treatment with PD-1 monoclonal antibody (mAb), pembrolizumab/MK-1375, followed by ibrutinib on endogenous immune function in previously untreated, high-risk CLL patients (defined as presence of del17p or TP53, del11q or ATM mutation, unmutated IGVH or mutated IGVH with 3.21 phenotype) with absolute lymphocyte count >20,000 but without meeting iwCLL criteria to start therapy.

Primary Objectives:

1. Assessment of the complete response (CR) of CLL to therapeutic intervention (defined per current iWCLL 2008 response criteria)
2. Time to response of CLL to therapeutic intervention (defined as time to achievement of response according to iWCLL 2008 criteria).

Secondary Objectives

1. Assessment of the overall response rate (ORR) [CR + PR] per iWCLL 2008 response criteria
2. Restoration of immune response as measured by:
 - a. Decreased markers of T-cell exhaustion
 - b. Increased of quantitative immunoglobulin levels and subtype
2. Safety and toxicity of the combination
3. Progression free survival (PFS)
4. 3. Incidence of Richter's transformation (defined as transformation of CLL into an aggressive lymphoid/histiocytic histology including well defined World Health Organization 2008 subtypes). Richter's transformation should be biopsy proven

Exploratory Objectives:

1. Alterations in T lymphocyte function, including changes in:
 - a. TH1:TH2 polarization, and TReg:TH17 distributions
 - b. Markers of T cell exhaustion and/or inhibition
 - c. Alterations in distribution of naïve vs. memory
 - d. Cellular activation and cell-mediated cytotoxic capacity
2. Alterations in B lymphocyte function, including changes in:
 - a. Serum anti-pneumococcal antibody titers in response to Prevnar vaccination
 - b. Quantitative serum immunoglobulin levels and subtyping
 - c. Fc-receptor (FcR) expression patterns
3. Alterations in global systemic cytokine patterns: Includes IFN- γ , TNF- α , IL-2, IL-4, IL-10, IL-6, IL-17A, allowing discrimination between TH1, TH2, and TH17 profiles (described in Section 4.2.2.2)

Hypothesis for Primary and Secondary Objectives:

The therapeutic combination of PD1:PDL1 blockade (PDB) and ibrutinib can improve the severe immune dysfunction classically associated with CLL, thereby improving disease-related morbidity and mortality in high-risk, previously untreated patients.

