4 STUDY DESIGN AND ENDPOINTS

4.1 DESCRIPTION OF THE STUDY DESIGN

Trial Design

The trial is an open-label, single arm phase II study to be conducted only at the Moffitt Cancer Center. Anticipated accrual will be 25 subjects. One of the secondary endpoint of this study is reconstitution of immune function, using response to pneumococcal vaccination as a clinical surrogate representation of global immune function. The study is designed to test the null hypothesis that, in high risk CLL (defined as presence of del17p or TP53, del11q or ATM mutation, unmutated IGVH or mutated IGVH with 3.21 phenotype) patients who do not require treatment of CLL and receive PD-1:PD-L1 blockade along with ibrutinib, challenge with the 7-valent pneumococcal vaccine will elicit an immunologic response <40%, defined as the generation of detectable antibody responses to >6 antigens. Our specified alternative hypothesis is that vaccination in the context of PD-1 blockade and ibrutinib will elicit an immunologic response >60% with 90% power.

Overall treatment Schema: All intravenous treatments will be administered at the outpatient Moffitt Cancer Center Infusion Center. The patients will receive a combination of IV pembrolizumab (anti-PD1) and oral ibrutinib according to the scheduled depicted in Figure 1. Briefly, patients will receive pembrolizumab on a 3-week interval schedule for a total of at least 51 weeks (it could be extended for up to 2 years if clinical benefit per investigator); starting with week 6, patients will additionally start daily oral ibrutinib which will be continued through 54 weeks of ibrutinib therapy. The rationale of starting pembrolizumab first is to avoid overlapping toxicity of ibrutinib and the anti-PD1 antibody.

Biomarker Research

Immune Monitoring Laboratory Correlates:

1. Global Immune function will be assessed in terms of serum cytokine patterns. Patient sera will be evaluated by flow cytometric means using cytokine bead arrays to measure serum cytokine levels quantitatively. The cytokine panel will include IFN- γ , TNF- α , IL-2, IL-4, IL-10, IL-6, IL-17A, allowing discrimination between TH1, TH2, and TH17 profiles.

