4.2.2 SECONDARY ENDPOINTS

1. Overall response rate (ORR) [CR + PR]
2. Restoration of immune response as measured by:

- a. Decreased markers of T-cell exhaustion
- b. Increased of quantitative immunoglobulin levels and subtype
- 2. Safety and toxicity of the combination
- 3. Progression free survival (PFS)
- 4. Incidence of Richter's transformation

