4.2.3 EXPLORATORY ENDPOINTS

- 1. Alterations of T-cell function: We postulate that there will be increased polarization towards TH1 compartment cells, which will be associated with increased cellular immunity. PD-1 blockage will increase TH1 mediated anti-tumor response.
- 2. Alterations in B-cell function: Combination of BTK and PD-1 inhibition will restore B-cell function
- 3. Alterations in cytokine profile (as defined in Section 4.2.2.2)
- 4. Evaluation of toxicity and safety of the combined therapy: In order to minimize toxicity, pembrolizumab will start 6 weeks prior to ibrutinib

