10 STATISTICAL CONSIDERATIONS

10.1 STATISTICAL AND ANALYTICAL PLANS

Enrolled patients will be evaluable for response assessment if receiving at least 4 weeks into ibrutinib therapy and at least 2 cycles of pembrolizumab. It will be used for efficacy and safety analysis. The primary endpoint of this trial is the complete response (CR) with the hypothesis of obtaining CR in 30% of patients and the secondary end point is the overall response rate (ORR, the immune response to the vaccine measured as T cell subset alterations, B-cell immune response potency to the vaccine and the cytokine patterns in treated patients. Exact binomial 95% confidence intervals for the true ORR will be calculated.

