10.2.4 EXPLORATORY ANALYSES

Biological samples for each of the 25 patients enrolled in the trial will be collected at 4 time-points. As the correlative experiments are not the primary focus of the study and are more exploratory in nature, no sample size / power calculations were completed. Summary statistics will be used to summarize the quantitative measures (e.g., cytokine levels, expression levels) for the patients at the 4 time-points with two-sample t-test use to determine if quantitative measurements differ between patients that response and patients that do not response at each time point. When assessing changes in quantitative measurements between time-points (e.g., pre and post treatment measurements) paired t-tests will be used. Longitudinal analysis with linear mixed models will also be used to look for statistical differences between the responders and non-responders using quantitative measurements at all 4 time-points. Correlation between quantitative measurements will be assessed with Spearman correlation.

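### The secondary endpoint on restored immune function is defined differently in 4.1, in 4.2.2 with 10.2.2, and in 10.1, and no section says which definition governs

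*Combined protocol and SAP*

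**What the plan says.** The current text describes the secondary immune endpoint in three ways.

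- **Section 4.1:** "One of the secondary endpoint of this study is reconstitution of immune function, using response to pneumococcal vaccination as a clinical surrogate representation". It adds a formal hypothesis, the null being that "challenge with the 7-valent pneumococcal vaccine will elicit an immunologic response <40%, defined as the generation of detectable antibody responses to >6 antigens". The alternative is above 60%, with 90% power and no significance level.
- **Section 4.2.2:** restored immune response is measured by "Decreased markers of T-cell exhaustion" and by increased immunoglobulin levels and subtype. The secondary objectives in section 3 and the summary agree. Section 10.2.2 tests change in exhaustion or inhibition markers and in serum immunoglobulins, using one-sided paired tests at p<0.05. It gives a detectable effect size of 0.60 with 25 patients.
- **Section 10.1:** beside overall response rate, "the immune response to the vaccine measured as T cell subset alterations, B-cell immune response potency to the vaccine and the cytokine patterns". It names neither exhaustion markers nor immunoglobulins. It also leaves out safety, PFS and Richter's transformation, which 4.2.2 lists.

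The exploratory lists overlap with these. Section 3 places TH polarization, cytokines and "Serum anti-pneumococcal antibody titers in response to Prevnar vaccination" under exploratory objectives. Section 4.2.3 lists T-cell function, B-cell function and cytokine profile as exploratory. Section 10.2.4 calls the correlative experiments "more exploratory in nature, no sample size / power calculations were completed" and gives cytokine levels as an example. Items 1b and 2b of the exploratory objectives, in section 3 and in the summary, repeat exhaustion markers and immunoglobulin levels, which are also secondary.

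**The concern.** Improving immune function is in the trial's title and is the stated hypothesis for the primary and secondary objectives, so a secondary claim about it will be read closely. The sets can disagree. Cytokines might shift while immunoglobulins do not rise and vaccine response stays below 40%. Under the 10.1 list the cytokine shift belongs to a secondary endpoint. Under 4.2.2 the secondary measures have not improved and the cytokine shift is an exploratory signal. With no stated precedence and no testing order, the label could be settled after the results are known, and a reader of the final report could not tell from the protocol which set was planned.

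**Working it through.** **1. Lists side by side**

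| Measure | 4.1 | 4.2.2 and 10.2.2 | 10.1 | Exploratory in |
|---|---|---|---|---|
| Vaccine response | secondary | absent | secondary (B-cell potency) | 3 and summary (titres) |
| Exhaustion markers | not named as an endpoint | secondary, tested | absent | 3 and summary, item 1b |
| Immunoglobulins | not named as an endpoint | secondary, tested | absent | 3 and summary, item 2b |
| T-cell subsets/polarization | not named as an endpoint | absent | secondary | 3, summary, 4.2.3 |
| Cytokines | not named as an endpoint | absent | secondary | 3, summary, 4.2.3, 10.2.4 |

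Section 4.1 also describes laboratory methods for the last four rows, but as correlates. No measure has the same label everywhere.

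**2. The plan's own figure for the 10.2.2 set**

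Inputs from 10.2.2: n = 25, effect size 0.60, one-sided 0.05. For a paired t-test the noncentrality is 0.60 × √25 = 3.0 on 24 degrees of freedom. Power = P(T(24; 3.0) > 1.711) = 0.898. The figure reproduces at about 90% power (exactly 90% needs 0.603). It supports the exhaustion and immunoglobulin tests only.

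**3. The 4.1 vaccine hypothesis at the planned size**

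Inputs: rates 0.40 and 0.60 from 4.1, and n = 25, assuming all 25 are vaccinated and evaluable. No significance level is stated, so several are shown. With X binomial(25, p), alpha = P(X ≥ r | 0.40) and power = P(X ≥ r | 0.60).

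| Success rule | One-sided alpha | Power |
|---|---|---|
| ≥15/25 | 0.034 | 58.6% |
| ≥14/25 | 0.078 | 73.2% |
| ≥12/25 | 0.268 | 92.2% |

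At 25 patients, 90% power is reached only at an alpha of about 0.27. A single-stage exact test with 90% power needs about 41 patients at one-sided 0.10, or 56 at 0.05 (levels assumed). Section 10 contains no test of this responder rate.

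**4. Scale of the opening (illustration)**

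Assume each of the three definitions is reduced to one test at one-sided 0.05, with equal correlation ρ between test statistics. The chance of at least one false positive is 1 − Φ₃(1.645, 1.645, 1.645; ρ).

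- ρ = 0: 1 − 0.95³ = 0.143
- ρ = 0.5: 0.118
- ρ = 0.8: 0.093

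One fixed definition with one test gives 0.05.

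**5. Primary analysis**

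The two-stage rule in 10.2.1 (stop at 1 or fewer of 16; reject at 4 or fewer of 25) gives type I error 0.095, power 0.903, expected size 20.37 and early-termination probability 0.515. This agrees with the plan and does not depend on the immune endpoints.

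**The case against.** The best defence is that 10.2.2 already settles the matter in practice. It is headed as the analysis of the secondary endpoints, it matches 4.2.2 and the secondary objectives in section 3 and the summary, and it is the only section that attaches secondary tests to immune measures. Against it stand one sentence in 10.1 and one paragraph in 4.1, and those two overlap because both centre on the vaccine. This stands to the extent that 10.2.2 is the natural definition to adopt. It does not remove the conflict: 10.1 is in the same statistical chapter, 4.1 presents its vaccine hypothesis as the basis of the design, and no section gives precedence.

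A reader might infer more than the documents support:

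- **That 10.1 controls, so the planned endpoint is the vaccine, T-cell-subset and cytokine set.** Nothing gives 10.1 that status.
- **That following 10.1 would produce a declared secondary success.** It contains no test, threshold or success rule for its immune measures. Its only stated analysis is a confidence interval for overall response. The likely harm is a mislabelled exploratory result, not a wrong trial decision.
- **That a promised 5% error rate is breached.** The 0.05 in 10.2.2 is a per-test level for that set, and no family-wise rate is promised. Section 4.1 names eight exhaustion markers, so one test per definition is a simplification. Counting seven cytokine tests would measure multiplicity within a set, which is a different question.
- **That 4.2.3 names vaccine titres as exploratory.** It names B-cell function. Titres appear in section 3 and the summary.
- **That selective reporting is intended.** The text shows an opening, not an intent.

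**Conclusion.** The point holds as a contradiction in the current text. The secondary immune endpoint has three non-matching definitions, and measures that are secondary in 10.1 or 4.1 are exploratory elsewhere. Section 10.2.2 is the best candidate for the operative definition, but the documents do not say so.

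The 0.09 to 0.14 range shows scale only. It rests on assumed single tests, an assumed common level and assumed correlations. The textual conflict does not depend on it. Separately, the 90% power in 4.1 is not attainable with 25 patients at the conventional one-sided levels shown. The complete-response analysis and its decision rule are untouched. The change should be made before immune data are examined.

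**What to change.** 1. Rewrite the secondary-endpoint sentence of 10.1 to repeat the 4.2.2 list: overall response rate, exhaustion markers, immunoglobulin levels, safety, PFS and Richter's transformation. State that any secondary conclusion on immune restoration rests only on the 10.2.2 tests of exhaustion markers and immunoglobulins.
2. In 10.1 and 4.1, label T-cell subsets, cytokines and vaccine response as exploratory, reported as estimates with 95% confidence intervals.
3. In 4.1, remove the statement that the study is designed to test the vaccine hypothesis with 90% power, or restate it for 25 patients with its significance level (58.6% at one-sided 0.034, or 73.2% at 0.078). If the responder definition is kept, reconcile the 7-valent vaccine in 4.1 with the 13-valent vaccine in 7.7.
4. Delete exhaustion markers and immunoglobulin levels from the exploratory lists (items 1b and 2b) in section 3 and the summary, so that each measure has one label.

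These are wording changes that need no new patients, samples or procedures. The cost is that a cytokine, T-cell-subset or vaccine result can no longer be presented as a secondary-endpoint success. Keeping vaccine response as a secondary test at 90% power would not be free: it would need the larger samples shown in the working.

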10.2 DESCRIPTION OF STATISTICAL METHODS

10.2.1 ANALYSIS OF THE PRIMARY EFFICACY ENDPOINT(S)

The Simon's minmax two-stage design will be used to test the null hypothesis that complete response (CR) \leq 10% versus the alternative that CR \geq 30% with 90% power and a type I error rate of 10%. This will result in an expected sample size of 20.37 and a probability of early termination of 0.52. After testing the drug combination on 16 patients in the first stage, the trial will be terminated if 1 or fewer respond. If the trial goes on to the second stage, a total of 25 patients will be studied. If the total number responding is less than or equal to 4, the drug combination will be rejected. Statistical analyses will be descriptive in nature. Patients' demographics, AEs and serious AEs, disease status, and CR will be summarized by descriptive statistics.

Clinical response rates will be calculated with 95% CIs.

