5.3 STRATEGIES FOR RECRUITMENT AND RETENTION

Recruitment of the 25 participants for this trial will occur from new or established patients treated at the Hematology Clinic at Moffitt Cancer Center. Screen failure is anticipated to be less than 10%. The target accrual is expected to be reached in 18-24 months. All faculty members in the Lymphoma Section will be sub-investigators on the trial. They will be trained on the trial design, study agents, and eligibility criteria. This will equip each investigator to discuss the trial with potential participants as appropriate. The trial will be listed on the Moffitt Cancer Center website (www.moffitt.org) for the availability of local physicians to refer patients who could be eligible for the trial.

All investigators will be made aware of the emphasis to enroll women and minorities. The design of the trial and eligibility criteria are not restrictive relative to women and minorities. As stated in the background section of the protocol, CLL affects more males than females (1.7:1) [2-4]. The clinical research team for this trial has experience with recruiting in another frontline investigator-initiated trial (MCC16622). Of the 45 participants accrued, 15 were women. The sex, ethnicity, and race of each participant on this trial will be captured in the Oncore electronic data base for reporting purposes.

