7.1.15 Tumor Imaging

Tumor imaging will consist of CT scan of the neck, chest, abdomen and pelvis. CT scan will be done at screening (if not done within 3 months prior to consent). Response assessments will be done at week 12 (+/-3 days), week 24 (+/-3 days), and after 51 weeks of ibrutinib. If the subject discontinues treatment early or progression of disease is suspected, CT will be done at the discretion of the investigator. Imaging during follow-up will be performed per investigator discretion.

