7.1.16 Bone Marrow Biopsy

A bone marrow biopsy will be performed at screening (if not performed within 30 days), after the end of pembrolizumab and ibrutinib therapy (28-35 days after week 51). If subject discontinues treatment early or progression of disease is suspected, a bone marrow biopsy will be done at the discretion of the investigator. During follow-up, bone marrow biopsies will be performed per investigator discretion.

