² Pembrolizumab infusions will be every 3 weeks (+/- 3 days) for 51 weeks. Ibrutinib will be dispensed every 3 weeks on the day of the pembrolizumab infusion. The last dispensing of ibrutinib will occur at week 51 and dosing will continue for an additional 3 weeks. A pill diary will be provided to participants with every dispensing of ibrutinib supply. Pill diary from previous dispensing will be reviewed for accountability.

³ Serum pregnancy test will be performed on females of childbearing potential (FCBP). A FCBP is considered when a sexually mature female: 1) has not undergone a hysterectomy or bilateral oophorectomy; or 2) has not been naturally postmenopausal for at least 12 consecutive months.

⁴ Hematology will consist of CBC and differential with platelet counts. CBC/differential will be performed at day 1, week 0,1,2 after starting pembrolizumab and then weekly for the first month on ibrutinib (weeks 6, 7, 8, 9, 10). Starting at week 12, CBC/diff will be performed on days of the clinic visits for physical examinations/drug administration. Further CBCs with differential will be performed per physician discretion.

⁵ CMP includes: sodium, potassium, chloride, CO2, calcium, BUN, creatinine, glucose, albumin, total protein, alkaline phosphatase, total bilirubin, AST/SGOT, ALT/SGPT, LDH. Subjects will have CMP , week 0, 1, 2 after starting pembrolizumab and then weekly for the first month on ibrutinib (weeks 6, 7, 8, 9, 10). Starting at week 12, CMP will be performed on days of the clinic visits for physical examinations/drug administration. Further CMPs will be performed per investigator discretion.

⁶ TLS (tumor lysis syndrome) laboratory assessment will include: BUN, creatinine, phosphorus, potassium, LDH, uric acid. TLS laboratory evaluation will occur at days 1-3 of week 0 weeks 1 and 2 after starting pembrolizumab and then weekly for the first month on ibrutinib (weeks 6, 7, 8, 9, 10). Further TLS assessments will depend on clinical condition and/or at investigator discretion.

⁷ Peripheral blood samples for ZAP-70, IgVH mutational status, and FISH testing will be done ONLY if not ever performed. Previous results must be available in the medical record for determination of eligibility.

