10.2.2 ANALYSIS OF THE SECONDARY ENDPOINT(S)

1. Change in T cell exhaustion and/or inhibition following treatment
2. Change in serum immunoglobulin levels following treatment
3. Progression free survival (PFS) and association with immune biomarkers

To determine if T cell exhaustion or inhibition have change due to treatment with the combination therapy at baseline immune testing to immune testing following completion of pembrolizumab and ibrutinib treatments (week 52) using paired t-tests with the null hypothesis being that there is no change in immune measurements following treatment (i.e., $H_0: \mu_d = 0$). If the assumptions of normality do not hold upon assessment, we will instead use nonparametric t-tests (i.e., Wilcoxon Sign Rank Test). Similar tests will be used to determine if changes in serum immunoglobulin levels also resulted following treatment. Tests will be one-sided as based on biology expect the change in immune response to be in one direction following treatment. Tests will be considered statistically significant if the p-value is less than 0.05. Assuming the study go on to stage II and enroll 25 patients, we will be able to detect a modest effect size of 0.60. To determine the association of progression free survival (PFS) with immune biomarkers (T cell exhaustion and/or inhibition, serum immunoglobulin levels), Cox proportional hazards models will be fit with assumption of proportional hazards (PH) assumption check via Schoenfeld residuals. If the PH assumption does not hold, we will rely on use of non-parametric methods (Kaplan-Meier curve with log-rank tests) where the biomarkers will be dichotomized for analysis based on an optimal cut-point determination based on an outcome-oriented approach outlined by Contral and O'Quigley (Contal C, O'Quigley J. An application of changepoint methods in studying the effect of age on survival in breast cancer. Computational Statistics & Data Analysis. 1999;30:253-70.). A Cox regression of the log hazard ratio on the continuous biomarker (assuming a standard deviation of 1 and an anticipated event rate of 0.50) will have 80% power at a 0.05 significance level to detect a regression coefficient equal to 0.79 (i.e., hazard ratio of 2.20).

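### Does the silence on when stage-1 complete response is read, and on holding accrual after patient 16, undermine the two-stage design?

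*Combined protocol and SAP*

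**What the plan says.** Section 10.2.1 specifies a Simon minimax design for CR, with a null rate of 10%, an alternative of 30%, type I error 10% and power 90%. The stage-1 rule is "After testing the drug combination on 16 patients in the first stage, the trial will be terminated if 1 or fewer respond". The stated properties are: "This will result in an expected sample size of 20.37 and a probability of early termination of 0.52". The second stage is conditional: "If the trial goes on to the second stage, a total of 25 patients will be studied". Section 10.2.2 uses the same condition when it gives a detectable effect: "Assuming the study go on to stage II and enroll 25 patients". Section 10.2.3 also treats the first 16 patients as a separate stage, and it contains the only explicit halt of accrual, which is for dose-limiting toxicity.

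On timing, Section 7.1.15 says: "Response assessments will be done at week 12 (+/-3 days), week 24 (+/-3 days), and after 51 weeks of ibrutinib". Section 7.1.16 places the only scheduled marrow after baseline "after the end of pembrolizumab and ibrutinib therapy (28-35 days after week 51"), that is, at weeks 55-56. A footnote in Section 7.3.7 adds: "The last dispensing of ibrutinib will occur at week 51 and dosing will continue for an additional 3 weeks". None of these visits is tied to the stage-1 decision. Section 10.1 sets a minimum exposure for evaluability, not a reading time.

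On the calendar, Section 5.3 says: "The target accrual is expected to be reached in 18-24 months". The Study Summary gives a study duration of three to four years and two years per participant.

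**The concern.** An expected sample size of 20.37 is an expected enrolment only if nobody beyond patient 16 enters before stage 1 is decided. Treatment lasts about a year and recruitment 18-24 months. A CR reading at the end of treatment therefore comes late relative to enrolment, and the plan has no written rule to stop entry in the meantime. Read that way, either the saving in patients disappears or, if accrual is paused, the recruitment period and study duration become too short.

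The population makes this matter more. Exclusion criterion 3 in Section 5.2 rules out patients who already meet criteria to start therapy, so limiting exposure to an inactive regimen is a real purpose of the early stop.

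**Working it through.** **Reproducing the stated design** (inputs from Section 10.2.1: 16 then 25 patients, stop at 1 or fewer CR, reject at 4 or fewer).

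- Probability of early termination at 10%: 0.9^16 + 16 × 0.1 × 0.9^15 = 0.1853 + 0.3294 = 0.5147. The plan prints 0.52, an immaterial rounding slip.
- Expected N at 10%: 16 + 9 × (1 − 0.5147) = 20.37, as stated.
- Exact type I error 0.095 and power 0.903, both within target.

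**Calendar.** Assume even accrual, so that patient k enters at k × A/25 months, with A = 18 or 24 (Section 5.3). Take 4.348 weeks per month.

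- Patient 16 enters at 16 × 18/25 = 11.52 or 16 × 24/25 = 15.36 months.
- The last nine patients take 9 × 18/25 = 6.48 or 9 × 24/25 = 8.64 months, about 28 or 38 weeks.
- Lag to reading: week 12 = 2.76 months, week 24 = 5.52, week 51 = 11.73, week 56 = 12.88.

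**Without a hold.** Number enrolled at the reading: m = whole part of (patient-16 entry + lag) × 25/A, capped at 25. Expected N under the null: 0.5147 × m + 0.4853 × 25.

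**With a full hold.** Expected N stays 20.37. For a trial that continues, accrual ends at A + lag. The study ends 24 months later (two years per participant).

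| Reading | A (months) | No hold: m | No hold: expected N | Hold: accrual ends (month) | Hold: study ends (month) |
|---|---|---|---|---|---|
| Week 12 | 18 | 19 | 21.91 | 20.8 | 44.8 |
| Week 12 | 24 | 18 | 21.40 | 26.8 | 50.8 |
| Week 24 | 18 | 23 | 23.97 | 23.5 | 47.5 |
| Week 24 | 24 | 21 | 22.94 | 29.5 | 53.5 |
| Weeks 51-56 | 18 | 25 | 25.00 | 29.7-30.9 | 53.7-54.9 |
| Weeks 51-56 | 24 | 25 | 25.00 | 35.7-36.9 | 59.7-60.9 |

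Counting 51 weeks of ibrutinib from its week-6 start puts the last scan at week 57, which leaves the no-hold result at 25.

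Against the stated 18-24 months of accrual and 36-48 months of study, a hold with a week-12 or week-24 reading fits at the faster rate and not at the slower one. A hold with an end-of-treatment reading fits at neither rate if all 16 readings are awaited.

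**The full hold is an upper case.** Once two CRs are documented, the stage-1 rule can no longer stop the trial, so there is no need to wait for the rest. With a week-55 reading and release at the second CR, the probability that a continuing trial finishes accrual within 24 months is about 0.24 (true CR 10%) or 0.60 (30%) at the faster rate, and 0.02 or 0.09 at the slower.

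**Which reading does the plan imply?** Appendix C describes CR through blood immunophenotyping, nodes, liver and spleen, symptoms and blood counts, and lists no marrow item. Time to response is also a primary endpoint (Section 4.2.1), so responses have to be dated as they occur. A reading before the end of treatment is therefore open under the text.

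**The case for a change.** The strongest case for a change is that staff could enrol straight through the stage-1 gate without breaching anything written. The plan does spell out an accrual halt for toxicity but none for efficacy. Section 5.5 lists futility as a ground for suspension, and Section 8.5 lets the monitoring committee suspend or close the study, but neither gives a trigger or a time. Without a hold, 20.37 is not reached at any scheduled assessment. A sentence or two would settle it at no cost in patients.

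Much of this stands: the omission is real and the arithmetic is right. A clarifying sentence would be good housekeeping.

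The claim that the expected N and the calendar cannot both hold does not stand. It needs an end-of-treatment reading that the plan never sets. The no-hold branch also sits badly with Sections 10.2.1 and 10.2.2, where having 25 patients depends on reaching stage 2. What remains is a recruitment forecast that looks optimistic if the reading is late or accrual slow. That forecast is an expectation, not a design parameter.

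**Conclusion.** No change to the plan follows. The two-stage rule is correctly derived, and its type I error (0.095), power (0.903) and maximum of 25 hold whenever stage 1 is read and whether or not accrual pauses. If the interim stop were ignored altogether, 5 or more CR in 25 would still give 0.098 and 0.910.

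What varies is the number enrolled under the null if nobody pauses (21.4-21.9 at week 12, 22.9-24.0 at week 24, 25 at end of treatment) and the length of the calendar if they do. The team can settle this by reading the design as Section 10.2.1 frames it, with patients 17-25 following a stage-1 pass. A long pause against enrolling further patients before the look is a trade-off on which reasonable statisticians differ.

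The figures assume even accrual over 18-24 months and, for study length, a full two years for the last patient. Counted only to the last CR reading at weeks 55-56, a full hold gives 43.3-49.8 months, which is not clearly outside three to four years.
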